9.6. Other Safety Data

9.6.1. Medication Errors

The number of dosing errors will be summarized for each medication error event (Overdose, Consumption of the study treatment by the wrong patient, Other) by visit and overall. All the other variables collected for study medication errors will be listed only.

9.6.2. ECOG Performance Score

ECOG performance score at each timepoint and its change from baseline will be summarized by treatment arm. The data will also be listed.

9.6.3. Exposure during pregnancy

Pregnancy outcomes during exposure will be handled outside this execution plan, and relevant details will be documented in the Clinical Study Report.

10. Pharmacokinetics

Pharmacokinetics and Immunogenicity will be treated in a separate analysis plan.

11. Interim Analysis

A DSMB is established with the responsibility of safeguarding the safety of study participants. The DSMB will review accumulating safety data during the conduct of the study and the interim analyses. The DSMB will provide ongoing review and recommendations to the Sponsor as necessary in relation to study conduct and patient management.

The DSMB charter will describe the operational aspects of the DSMB and the analytical and monitoring plan for the study. The Charter will further state the primary responsibilities of the DSMB, its relationship with Polyphor, its membership, and the purpose and timing of its meetings, statistical monitoring guidelines to be implemented, and statistical analysis for open and closed sessions. The DSMB Charter and meeting minutes will be submitted as part of the final Clinical Study Report.

12. Changes in the Planned Analysis

The changes from planned analyses described in the protocol and in the Statistical Analysis Plan (SAP) version 1.4 dated 18Jan2019 to those presented in this execution plan are the followings:

- Added PP set definition and analysis of coprimary endpoints: PFS and OS in PP (3rd line+ confirmed) set. Clarified definition of 3rd line+ Confirmed in analysis sets is based on randomization strata and eCRF data.
- Added sensitivity analysis for PFS and OS in ITT 3rd line+ (ITT 3rd line+ Confirmed and PP 3rd line+ Confirmed).
- Added sensitivity analysis for ORR in RE 3rd line+ (RE 3rd line+ Confirmed).
- Data listings for prior systemic cancer/oncology therapies will include only dose, unit, dose regimen, frequency, best response to cancer therapy, and reason for discontinuation (toxicity, other or progressive disease).
- For this study, up to three (3) intervening NEs will be allowed to confirm a CR or PR. Subsequent documentation of a CR may provide confirmation of a previously identified CR with up to three (3) intervening non- evaluable (NE) assessments (e.g. CR NE CR, CR NE NE NE OR, or CR NE NE NE CR). Similarly, subsequent documentation of a PR may provide confirmation of a previously identified PR with up to three (3) intervening NEs (e.g., PR NE PR, PR NE NE PR, or PR NE NE NE NE PR). However, only one (1) intervening SD will be allowed between PRs for confirmation (i.e., PR SD PR).
- Listing of patients with clinically significant abnormalities in vital signs has been removed.
- All AESIs and only the non-overlapping categories for AEPIs will be summarized by treatment arm, MedDRA SOC, Preferred term, and toxicity grade.
- Prior anticancer therapies will not be summarized as regimens since regimens are not identified in eCRF. Individual therapies instead of regimens will be reported.
- Subgroups have been updated in the exploratory efficacy endpoints, section 8.5.
- COVID section added
- Medication errors will not be reported by MedDRA. Instead, they will be reported by medication error event overall and at each visit.

13. References

- Ellis S, Carroll KJ and Pemberton K. Analysis of Duration of Response in Oncology Trials. Contemporary Clinical Trials, 2008; 29: 456-465.
- Carroll, KJ. Back to basics: explaining sample size in outcome trials, are statisticians doing a thorough job? Pharm Stats, 2009; 8: 333–345.
- Dixon D and Simon R. Bayesian Subset Analysis. Biometrics, 1991; 47:871-881.
- MedDRA Dictionary (https://www.meddra.org/)
- NCI CTCAE Grade
 https://ctep.cancer.gov/protocolDevelopment/electronic_applications/ctc.htm

- Sampson HA. Second Symposium on the Definition and Management of Anaphylaxis: Summary Report—Second National Institute of Allergy and Infectious Disease/Food Allergy and Anaphylaxis Network Symposium. Annals of Emergency Medicine. 2006;47(4):373-80.
- FDA 2009. Guidance for industry. Drug-induced livery injury: premarketing clinical evaluation.

 $\underline{http://www.fda.gov/downloads/Drugs/GuidanceComplianceRegulatoryInformation/Guidances/UCM174090.pdf}$

14. Appendices

14.1. General Schedule of Assessments

14.1.1. Schedule of Assessments for Balixafortide + Eribulin Treatment Arm

Table 2 - Schedule of Assessments for Balixafortide + Eribulin Treatment Arm: Screening, Cycle 1, and Cycle 2

Visits (Visit	ng -1)					Active t	reatmen	t phase (21 Days	per cycl	e)			
Window days)	reeni 1 to -			Сус	cle 1					-	Cycle 2	2	_	
	Sc.)	D1	D2	D3	D8	D9	D10	D1	D2	D3	D8	D9	D10	D21
Assessment		DI	02		10	D 7	D 10	DI	172		10		D10	021
Informed consent	Х													
IWRS/IRT	Х	Х	Х	Х	Х	Х	Х	Х	Х	Х	Х	Х	Х	
Inclusion/exclusion criteria	Х													
Demographics (gender, date of birth, race, ethnicity) and baseline data	Х													
Medical history	Х													
Patient reported health outcomes	Х	Х						Х						
Physical examination ^[1]	X ^[2]	X[3]						X ^[3]						
Vital signs (body temperature, resting blood pressure, respiratory rate, pulse rate) ^[1]	Х	Х						Х						
Weight, height ^[4]	Х	Х						Х						
ECOG performance status	Х	Х						Х						
Adverse events	X ^[5]	X												X
Prior/Concomitant medications	X	X												X
Clinical Laboratory tests ^[1]	X ^[6]	X ^[7]			X ^[7]			X ^[7]			X ^[7]			

Visits (Visit	ng (1)					Active t	reatmen	t phase ((21 Days	per cyc	le)			
Window days)	reeniı 1 to -			Сус	cle 1						Cycle	2		
	Sc) (-2	D1	D2	D3	D8	D9	D10	D1	D2	D3	80	Пŷ	D10	D21
Assessment		DI	D2	105	D0	D 7	D10	D 1	D2	105	100		DIU	021
Pregnancy test	X ^[8]	X ^[9]						X ^[9]						
Contraceptive advice	Х													
CT/MRI scan ^[10, 11]	X ^[12]													X[10]
Bone scan	X ^[12, 13]													
12-lead ECG ^[1]	Х	Х	Х			Х			X ^[14]			X ^[14]		
Document date and results of last tumor biopsy/fresh tumor biopsy	Х													
Blood for PK			Х		Х	Х			Х		Х	Х		
Blood for immunogenicity testing		Х			Х			Х			Х			
Blood for exploratory biomarkers in all patients ^[15]		Х	Х	Х	Х	х								
Confirmation of eligibility and randomization		Х												
Balixafortide treatment ^[16]		Х	Х	X	X	X	X	Х	Х	Х	Х	Х	X	
Eribulin treatment			Х			Х			Х			Х		
For patients at selected sites														
Optional tumor biopsy ^[17]	Х											X[18]		
Blood for other exploratory biomarkers		Х	Х		X							X ^[19]		

MRI: magnetic resonance imaging; RECIST: Response Evaluation Criteria In Solid Tumors; SAE: serious adverse event. Footnotes:

- 1. Additional assessments to those scheduled for this study should be performed as indicated at the Investigator's discretion (e.g. due to concerns about patient safety, patient's clinical status); the findings of an unscheduled examination should be recorded in the patient's source data and eCRF.
- 2. Standard, complete physical examination.
- 3. Targeted physical examination.

- 4. Height will be measured at Screening only.
- 5. SAEs will be recorded from the date that the informed consent form is signed.
- 6. Screening blood tests should be taken within 7 days prior to randomization.
- 7. Blood test results must be available within 24 hours prior to study medication administration.
- 8. Serum pregnancy test for women of childbearing potential only, no more than 7 days prior to Randomization. More frequent assessments can be performed if medically indicated as determined by the Investigator, and these evaluations will be recorded in the patient's source data and eCRF.
- 9. Urine pregnancy test for women of childbearing potential only.
- 10. CT/MRI scan will be performed at Screening, then from the date of randomization every 6 weeks (±7 days) during the first year, and then every 12 weeks (±7 days), thereafter, until PD is documented by RECIST v1.1. It is critical that tumor assessments are performed according to the Study Schedule in a timely and complete manner regardless of any dosing delay or interruption. Imaging assessments will be scheduled using the randomization date as the reference date for all timepoints and NOT scheduled according to the date of the previous timepoint. A delay in the imaging assessment to accommodate a treatment delay is not permitted. Following initial documentation of an objective response, a confirmatory CT/MRI scan will be performed at least 4 weeks later.
- 11. At the discretion of the Investigator, additional radiographic tumor assessments may be done at any time if there is clinical suspicion of disease progression; the results of the unscheduled scan should be recorded in the patient's source data and eCRF.
- 12. Record date and results of last scan on the patient's source data and eCRF. If no scan has been performed in the 30 days prior to Randomization a scan should be performed during Screening.
- 13. From the date of randomization, additional bone scans will be performed at the discretion of the Investigator.
- 14. After Cycle 2, the frequency of ECGs can be reduced to every 2 cycles if deemed clinically appropriate (i.e. absence of ECG findings in earlier assessments).
- 15. Blood will be collected from all patients to assess plasma levels of interferon gamma and additional cytokine markers.
- 16. Patients will start study medication within 3 days from randomization.
- 17. Patients at selected sites can optionally consent to fresh tumor biopsy at Screening and subsequent timepoints. If a biopsy has already been performed within 30 days prior to Randomization and tumor tissue is still available, then the fresh tumor biopsy is not required during Screening.
- 18. Alternatively, can be performed on Day 10 if preferred.
- 19. A blood sample will be taken only in patients at selected sites who are scheduled to have an optional, fresh tumor biopsy; the blood sample can be taken before or after the biopsy.

						Acti	ve treatm	ent pha	se (21 Day	ys per cy	cle)					Post-	treatment	phase
Visits (Visit Window days)		Cycle 3 Subsequent Cycles											EoT (+7)	30-day safety FU (+7)	Long- term FU (±7) ^[1]			
	D1	D2	D2	D4	D5	D9	D0	D10	D1	D2	D2	D9	D0	D10	D21			
Assessment	D 1	D2	05	104	03	Do	D9		DI	02		Do	D9		D21			
IWRS/IRT	Х	Х	X			Х	Х	X	Х	Х	X	Х	Х	X		Х		
Patient reported health outcomes	Х								Х							Х		
Targeted physical examination ^[2]	х								Х							Х		
Vital signs (body temperature, resting blood pressure, respiratory rate, pulse rate) ^[2]	Х								х							Х		
Weight	Х								Х							Х		
ECOG performance status	Х								Х							Х		
Adverse events	X-																Х	
Prior/Concomitant medications	X															Х	X ^[3]	
Clinical Laboratory tests ^[2]	X ^[4]					X ^[4]			X ^[4]			X ^[4]				Х		
Pregnancy test	X ^[5]								X ^[5]							X ^[5]		
CT/MRI scan ^[6, 7]															X[6]	X[8]		X[1]
Bone scan ^[9]																		
12-lead ECG ^[2]		X ^[10]					X ^[10]			X ^[10]			X ^[10]			Х		
Blood for PK		Х		X ^[11]	X ^[11]					X ^[12]	X ^[12]							
Blood for immunogenicity testing	х								X ^[13]							Х		

Table 3 - Schedule of Assessments for Balixafortide + Eribulin Treatment Arm: Cycle 3, Subsequent Cycles, and Post-treatment Phase

						Acti	ve treatm	ent pha	se (21 Day	/s per cy	cle)					Post-	treatment	phase
Visits (Visit Window days)				C	ycle 3						Subse	equent (Cycles			EoT (+7)	30-day safety FU (+7)	Long- term FU (±7) ^[1]
	D1	D2	D3	D4	D5	D8	ПQ	D10	D1	D2	D3	D8	D 0	D10	D21			
Assessment	DI	D2	03	54	03	100	D7	D10	D 1	D2	05	100	D 7		021			
Blood for exploratory biomarkers in all patients ^[14]	Х	х	x	X ^[15]	X ^[15]	Х	Х											
Balixafortide treatment	Х	Х	X			Х	Х	X	Х	Х	Х	Х	Х	Х				
Eribulin treatment		X					Х			Х			Х					
Document reason for treatment discontinuation																Х		
Survival status, PD monitoring, all anticancer medicines received																		x
For patients at selected sites																		
Optional tumor biopsy																Х		
Blood for other exploratory biomarkers	Х	x														Х		

AE: adverse event; MRI: magnetic resonance imaging; RECIST: Response Evaluation Criteria In Solid Tumors. Footnotes:

 Regardless of treatment arm, patients discontinued from study medication for any reason, in the absence of PD, will undergo repeat imaging and tumor response assessments (including CT/MRI scans) every 8 weeks ±7 days (every 12 weeks ±7 days if the patient has been on the study for ≥1 year) until PD is documented as per RECIST v1.1, or death occurs, or the patient is lost to follow-up, or the patient withdraws consent (whichever occurs first). Once PD is recorded, the patient will be followed every 6 months (or more frequently) for Survival Follow-up only, until the patient dies, withdraws consent, or is lost to follow-up (whichever occurs first). Survival follow-up can be conducted by telephone.

- 2. Additional assessments to those scheduled for this study should be performed as indicated at the Investigator's discretion (e.g. due to concerns about patient safety, patient's clinical status); the findings of an unscheduled examination should be recorded in the patient's source data and eCRF.
- 3. Concomitant therapy/medications taken since previous visit to be recorded for patients with unresolved AEs.
- 4. Blood test results must be available within 24 hours prior to study medication administration.
- 5. Urine pregnancy test for women of childbearing potential only.
- 6. CT/MRI scan will be performed at Screening, then from the date of randomization every 6 weeks (±7 days) during the first year, and then every 12 weeks (±7 days), thereafter, until PD is documented by RECIST v1.1. It is critical that tumor assessments are performed according to the Study Schedule in a timely and complete manner regardless of any dosing delay or interruption. Imaging assessments will be scheduled using the randomization date as the reference date for all timepoints and NOT scheduled according to the date of the previous timepoint. A delay in the imaging assessment to accommodate a treatment delay is not permitted. Following initial documentation of an objective response, a confirmatory CT/MRI scan will be performed at least 4 weeks later.
- 7. At the discretion of the Investigator, additional radiographic tumor assessments may be done at any time if there is clinical suspicion of disease progression; the results of the unscheduled scan should be recorded in the patient's source data and eCRF.
- 8. CT/MRI scans will be performed in patients who are discontinued from study medication in the absence of PD; however, patients who have already demonstrated objective PD (according to RECIST v 1.1) do not need to have scans repeated at the EoT visit.
- 9. From the date of randomization, additional bone scans will be performed at the discretion of the Investigator.
- 10. After Cycle 2, the frequency of ECGs can be reduced to every 2 cycles if deemed clinically appropriate (i.e. absence of ECG findings in earlier assessments).
- 11. For patients at selected sites only.
- 12. Cycle 5 and Cycle 7 only.
- 13. After Cycle 3, blood samples are taken on Day 1 of every alternate cycle (e.g. Cycle 5, Cycle 7, Cycle 9 etc).
- 14. Blood will be collected from all patients to assess plasma levels of interferon gamma and additional cytokine markers.
- 15. Only in patients at selected sites scheduled to have PK sampling.

14.1.2. Schedule of Assessments for Eribulin Monotherapy Treatment Arm

	ng 1)			Ac	tive treat	ment pha	ase (21 D	ays per c	ycle)			Ро	st-treatment	phase
	reeni 1 to -	Cyc	cle 1		Cycle 2		Су	cle 3	Subs	equent (Cycles		30-day	
	Sci (-2	D2	D0	D2	D0	D21	D2	D0	D2	D0	D21	EOT (+7)	safety FU	Long-term FU (±7) ^[1]
Assessment		D2	09	D2	09	D21	D2	09	D2	D9	D21	()	(+7)	
Informed consent	Х													
IWRS/IRT	Х	Х	Х	Х	Х		Х	Х	Х	Х		Х		
Inclusion/exclusion criteria	Х													
Demographics (gender, date of birth, race, ethnicity) and baseline data	Х													
Medical history	Х													
Patient reported health outcomes	Х	Х		Х			Х		Х			Х		
Physical examination ^[2]	X ^[3]	X ^[4]		X ^[4]			X ^[4]		X ^[4]			X ^[4]		
Vital signs (body temperature, resting blood pressure, respiratory rate, pulse rate) ^[2]	Х	Х		Х			Х		Х			Х		
Weight, height ^[5]	Х	Х		Х			Х		Х			Х		
ECOG performance status	Х	Х		Х			Х		Х			Х		
Adverse events	X ^[6]	X											X	
Prior/Concomitant medications	Х	X										X	X ^[7]	
Clinical laboratory tests ^[2]	X ^[8]	X ^[9]	X ^[9]	X ^[9]	X ^[9]		X ^[9]	X ^[9]	X ^[9]	X ^[9]		Х		
Pregnancy test	X ^[10]	X ^[11]		X ^[11]			X ^[11]		X ^[11]			X ^[11]		
Contraceptive advice	Х													
CT/MRI scan ^[12,13]	X ^[14]					X ^[12]					X ^[12]	X ^[15]		X[1]
Bone scan	X ^[14, 16]													
12-lead ECG ^[2]	Х	Х	Х	X [17]	X[17]		X[17]	X[17]	X ^[17]	X ^[17]		Х		
Document date and results of last tumor biopsy/fresh tumor biopsy	Х													

	ing -1)			Ac	tive treatn	nent pha	ise (21 Da	iys per c	ycle)			Pos	st-treatment	phase
	reeni 21 to	Сус	ele 1		Cycle 2		Сус	ele 3	Subse	equent C	ycles		30-day	
	Sc (-2	D2	D9	D2	D9	D21	D2	D9	D2	D9	D21	EOT (+7)	safety FU	Long-term FU (±7) ^[1]
Assessment		02	D 7	02	D 7	D21	D2	D 7	02	D 7	D21		(+7)	
Blood for exploratory biomarkers in all patients ^[18]		Х	Х				Х	х						
Confirmation of eligibility and randomization		Х												
Eribulin treatment ^[19]		Х	Х	Х	X		Х	Х	Х	Х				
Document reason for treatment discontinuation												Х		
Survival status, PD monitoring, all anticancer medicines received														X
For patients at selected sites														
Optional tumor biopsy ^[20]	Х				Х							Х		
Blood for other exploratory biomarkers		Х			X ^[21]		Х					Х		

AE: adverse event; RI: magnetic resonance imaging; RECIST: Response Evaluation Criteria In Solid Tumors; SAE: serious adverse event. **Footnotes:**

- Regardless of treatment arm, patients discontinued from study medication for any reason, in the absence of PD, will undergo repeat imaging and tumor response assessments (including CT/MRI scans) every 8 weeks ±7 days (every 12 weeks ±7 days if the patient has been on the study for ≥1 year) until PD is documented as per RECIST v1.1, or death occurs, or the patient is lost to follow-up, or the patient withdraws consent (whichever occurs first). Once PD is recorded, the patient will be followed every 6 months (or more frequently) for Survival Follow-up only, until the patient dies, withdraws consent, or is lost to follow-up (whichever occurs first). Survival follow-up can be conducted by telephone.
- 2. Additional assessments to those scheduled for this study should be performed as indicated at the Investigator's discretion (e.g. due to concerns about patient safety, patient's clinical status); the findings of an unscheduled examination should be recorded in the patient's source data and eCRF.
- 3. Standard, complete physical examination.

- 4. Targeted physical examination.
- 5. Height will be measured at Screening only.
- 6. SAEs will be recorded from the date that the informed consent form is signed.
- 7. Concomitant therapy/medications taken since previous visit to be recorded for patients with unresolved AEs.
- 8. Screening blood tests should be taken within 7 days prior to randomization.
- 9. Blood test results must be available within 24 hours prior to study medication administration.
- 10. Serum pregnancy test for women of childbearing potential only, no more than 7 days prior to Randomization. More frequent assessments can be performed if medically indicated as determined by the Investigator, and these evaluations will be recorded in the patient's source data and eCRF.
- 11. Urine pregnancy test for women of childbearing potential only.
- 12. CT/MRI scan will be performed at Screening, then from the date of randomization every 6 weeks (±7 days) during the first year, and then every 12 weeks (±7 days), thereafter, until PD is documented by RECIST v1.1. It is critical that tumor assessments are performed according to the Study Schedule in a timely and complete manner regardless of any dosing delay or interruption. Imaging assessments will be scheduled using the randomization date as the reference date for all timepoints and NOT scheduled according to the date of the previous timepoint. A delay in the imaging assessment to accommodate a treatment delay is not permitted. Following initial documentation of an objective response, a confirmatory CT/MRI scan will be performed at least 4 weeks later.
- 13. At the discretion of the Investigator, additional radiographic tumor assessments may be done at any time if there is clinical suspicion of disease progression; the results of the unscheduled scan should be recorded in the patient's source data and eCRF.
- 14. Record date and results of last scan on the patient's source data and eCRF. If no scan has been performed in the 30 days prior to Randomization a scan should be performed during Screening.
- 15. CT/MRI scans will be performed in patients who are discontinued from study medication in the absence of PD; however, patients who have already demonstrated objective PD (according to RECIST v 1.1) do not need to have scans repeated at the EoT visit.
- 16. From the date of randomization, additional bone scans will be performed at the discretion of the Investigator.
- 17. After Cycle 2, the frequency of ECGs can be reduced to every 2 cycles if deemed clinically appropriate (i.e. absence of ECG findings in earlier assessments).
- 18. Blood will be collected from all patients to assess plasma levels of interferon gamma and additional cytokine markers.
- 19. Patients will start study medication within 3 days from randomization.
- 20. Patients at selected sites can optionally consent to fresh tumor biopsy at Screening and subsequent timepoints. If a biopsy has already been performed within 30 days prior to Randomization and tumor tissue is still available, then the fresh tumor biopsy is not required during Screening.

21. A blood sample will be taken only in patients at selected sites who are scheduled to have an optional, fresh tumor biopsy; the blood sample can be taken before or after the biopsy.

14.2. Type I Error Control for Primary and Key Secondary Efficacy Analyses

Figure 1 - Type I Error Control for Primary and Key Secondary Efficacy Analyses in the 3rd line+ patient population

			t	ORR est at a;=0.001					
		+ve	-				-ve	-	
		3rd line+ PFS test a OS at interim test a	t a;=0.040 t a;=0.002				3rd line-t PFS test at OS at interim test at	CL=0.040 t CL=0.001	
Г	3rd line -ve @ a	+ PFS a;=0.040	3rd line+ PFS +ve @ a;=0.040	_	Γ	3rd line -ve @ a	+ PFS =0.040	3rd line+ PFS +ve@ CL=0.040	-
	Overall PFS not	PopIn tested	overall PopIn test at a;c0.040	_	30	Overall PFS not	- PopIn tested	Overall PopIn test at a;=0.040	-
┝	nterim OS-ve	Final OS test @ a=0.008	Overall PopIn PFS-ve and Interim OS-ve	Final OS test at a;:0.008		Interim 05-ve	Final OS test @ a.=0.008	Overall PopIn PFS-ve and Interim OS-ve	Final OS test ata;=0.008
L	Interim OS+ve	Final OS test @ a=0.010	Overall PopIn PFS-ve and Interim OS+ve	Final OS test at CL=0.0111>		Interim OS+ve	Final OS test @ a.=0.009	Overall PopIn PFS -ve and Interim OS+ve	Final OS test at a=0.009
			Overall PopIn PFS+ve andInterim OS-ve	Final OS test at CL=0.048				Overall PopIn PFS+ve and Interim 05-ve	Final OS test ata;=0.048
			Overall PopIn PFS+ve andInterim OS +ve	Final OS test at CL=0.050				Overall PopIn PFS+ve and Interim OS+ve	Final OS test at a;=0.049

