12.3.7 Efficacy Analyses

12.3.7.1 Co-Primary Endpoints: Objective Response Rate and Progression Free Survival

Objective Response Rate

Will be analyzed in the 3rd line + population in the same fashion as for the overall, 2nd line + population. The alpha allocation will be 0.001 2-sided.

Progression Free Survival

Will be analyzed in the 3rd line+ population in the same fashion as for the overall, 2nd line + population. The alpha allocation will be 0.040 2-sided. If PFS in the 3rd line + population is met at the allocated alpha level, PFS in the overall population will also be formally tested at the same alpha level.

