8.2. Key Secondary Efficacy Endpoint Analysis

OS is the key secondary endpoint. The alpha allocation will be between 0.001 and 0.002 2-sided at the interim and between 0.008 and 0.050 at the final analysis depending on the results of previous analyses PFS and ORR analyses as illustrated in the flow diagram of section 14.2.

OS defined as the time from the date of randomization to death from any cause will be assessed in the ITT (3^{rd} line+) set. The ITT (3^{rd} line+ confirmed) and PP (3^{rd} line+ confirmed) sets will also be analyzed as sensitivity. Patients will be followed until their date of death, lost to followup, withdrawal of consent, or end of study.

Patients who are lost to follow-up or are not known to have died at the time of data-cut-off for analysis will be censored at later of last visit date, or last known alive date.

Patients who do not have any follow up since randomization will be censored at the date of randomization.

The duration of overall survival will be calculated for all randomized patients as follows:

- For patients who have died: Duration of overall survival = Date of death Date of randomization + 1 day;
- For patients who are lost-to-follow-up or not known to have died: Duration of overall survival = Later of Date of last visit date, last date known to be alive Date of randomization + 1 day;

See section 4.4 for details on how to handle partial death date.

OS will be analyzed using the same Cox proportional hazards model as PFS. The CI coverage for OS at the planned interim and at the final analysis will be determined by the allocated alpha level.

A supportive analysis for OS will be conducted using a stratified log rank test for the ITT (3rd line+) set again as per the analysis of PFS; strata will be the randomization stratification factors as described in Section 8.1.3 for PFS.

The OS proportion at 6, 12 and 18 months, including 95% CIs, will also be presented.

8.3. Timing of Analyses of Primary and Key Secondary Efficacy Endpoints and Type I Error control

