In the 3rd line+ population co-primary efficacy endpoints are ORR and PFS; the key secondary efficacy endpoint is OS. A formal analysis of ORR is planned once all 3rd line+ patients have been randomized and followed for a minimum of 6 months. The formal analysis of PFS will take place once 286 PFS events have accrued, being expected when all randomized patients in the 3rd line+ strata have been followed for a minimum of 12 months. The alpha allocation for the PFS analysis will be 0.040 2-sided; if the PFS in the 3rd line+ population meets the allocated alpha level, PFS in the overall population will also be formally tested at the same alpha level; further, at the time of the PFS analysis an interim analysis of OS will be performed with an alpha allocation of 0.001 to 0.002 2-sided, depending on the result of the previous ORR analysis. The final analysis of OS will take place once all randomized patients have been followed for a minimum of 24 months at which time 226 events are expected. The alpha allocation for this analysis will be between 0.008 and 0.05 2-sided depending on the results of previous analyses. Thus, there will be 4 formal efficacy analyses in the 3rd line+ population (ORR, PFS, interim OS and final OS). If PFS is met in the 3rd line+ population, PFS analysis will be performed in the overall population. Consequently, there will be a total of 5 formal efficacy analyses. The overall Type I error rate will be controlled at 0.05 across these formal analyses by means of alpha allocation and recycling as described in Figure 1 in Appendix 14.2.

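### SAP Figure 1 re-tests OS after OS has already been won at the interim, and sets the final OS level by subtraction; error is controlled, but the rule should be corrected (low priority)

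*SAP*

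**What the plan says.** SAP 8.3 lists interim OS and final OS as two of the formal analyses in the 3rd line+ population and states "The overall Type I error rate will be controlled at 0.05 across these formal analyses by means of alpha allocation and recycling". The levels are:

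- ORR: "The alpha allocation will be 0.001 2-sided" (protocol 12.3.7.1).
- PFS: "The alpha allocation for the PFS analysis will be 0.040 2-sided" (SAP 8.3).
- Interim OS, at the PFS cut: "interim analysis of OS will be performed with an alpha allocation of 0.001 to 0.002 2-sided, depending on the result of the previous ORR analysis" (SAP 8.3).
- Final OS: "The alpha allocation for this analysis will be between 0.008 and 0.05 2-sided depending on the results of previous analyses" (SAP 8.3).

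Figure 1 in SAP 14.2 shows how the final level is reached. If either PFS test fails and interim OS was negative, the cell reads "Final OS test @ a=0.008". If interim OS was positive and ORR was positive, it reads "Final OS test @ a=0.010"; with ORR negative it is 0.009. If both PFS tests succeed, the final level is 0.048 after a negative interim, and 0.050 or 0.049 after a positive one. One cell is garbled in the extracted text, but the pattern is clear from the others.

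SAP 8.2 ties the interval to the same levels: "The CI coverage for OS at the planned interim and at the final analysis will be determined by the allocated alpha level".

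**The concern.** Interim and final OS test one null hypothesis in one analysis set, ITT (3rd line+). Alpha released by a rejected hypothesis can be recycled only to a different hypothesis. Once OS is rejected at the interim, nothing remains to be tested, yet Figure 1 sets a level that the final analysis can miss. OS could be declared positive and then reported as not significant at 0.010, with a 99% interval that includes 1. The documents have no explicit sentence for that sequence, and a choice made after the data are seen would be data-driven.

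The negative-interim cells have a milder fault. Subtracting the interim alpha from the OS total is a Bonferroni split. It takes no account of the fact that all interim deaths are also in the final analysis, so part of the OS allocation is never used.

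**Working it through.** **Inputs.** From SAP 4.1: median OS 14.4 v 17.4 months (ratio 14.4/17.4 = 0.828); 320 patients, 1:1; 12-month accrual with eta = 2, so entry density 2u/144; PFS analysis (and interim OS) at about month 24; final OS 12 months later, with 226 deaths expected. No dropout rate is given and none is used. Alpha levels are as listed above.

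**1. The plan's own total.** ORR negative: 0.001 + 0.040 + 0.001 + 0.008 = 0.050. ORR positive: 0.040 + 0.002 + 0.008 = 0.050. The 0.05 reproduces exactly. Each positive-interim level is the negative-interim level plus the interim alpha: 0.008 + 0.001 = 0.009, 0.008 + 0.002 = 0.010, 0.048 + 0.001 = 0.049, 0.048 + 0.002 = 0.050. In the figure, the 0.05 ceiling quoted in the text is reached only after a positive interim OS.

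**2. Deaths at each look.** D(T) = ∫ from 0 to 12 of (2u/144) × 160 × [(1 − 2^(−(T−u)/14.4)) + (1 − 2^(−(T−u)/17.4))] du.

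- D(36) = 225.3, against the SAP's 226.
- D(24) = 160.1. The documents state no interim count.
- Information fraction t = 160.1/225.3 = 0.711; correlation √t = 0.843.

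**3. OS alpha actually used.** Under the null this is P(|Z1| ≥ c1 or |Z2| ≥ c2), with (Z1, Z2) bivariate normal, correlation 0.843, c1 set by the interim level and c2 by the negative-interim final level. The level that uses the full allocation solves the same expression for c2 with the probability set to the OS total.

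| ORR; PFS tests | Interim level | Final level after negative / positive interim | OS alpha used | Unspent | Final level using full total |
|---|---|---|---|---|---|
| negative; either fails | 0.001 | 0.008 / 0.009 | 0.0083 | 0.0007 | 0.0087 |
| positive; either fails | 0.002 | 0.008 / 0.010 | 0.0088 | 0.0012 | 0.0093 |
| negative; both succeed | 0.001 | 0.048 / 0.049 | 0.0480 | 0.0010 | 0.0490 |
| positive; both succeed | 0.002 | 0.048 / 0.050 | 0.0481 | 0.0019 | 0.0499 |

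Over t = 0.55 to 0.75 the unspent amount runs from about 0.0005 to 0.0019.

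**4. Win, then failed re-test, at hazard ratio 0.828.** Mean of Z2 = |ln 0.828| × √226 / 2 = 0.1887 × 15.03 / 2 = 1.419. Mean of Z1 = 1.419 × 0.843 = 1.196. P(interim win) = Φ(1.196 − 3.291) = 1.8% at 0.001, and Φ(1.196 − 3.090) = 2.9% at 0.002. The joint probability P(|Z1| ≥ c1, |Z2| < c2), with c2 now the positive-interim level, gives:

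| Interim, then re-test | Unconditional | Given a win |
|---|---|---|
| 0.002, then 0.010 | 0.30% | 10% |
| 0.001, then 0.009 | 0.12% | 7% |
| 0.002, then 0.050 | 0.03% | 0.9% |
| 0.001, then 0.049 | 0.01% | 0.4% |

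These figures take each branch's levels as given and do not multiply by the chance of landing in that branch. At t = 0.55 the largest unconditional value is about 0.4%.

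**5. OS power at 0.828, subtracted level against full-allocation level.** 11.0% to 11.6% (total 0.009), 11.2% to 12.2% (0.010), 28.9% to 29.2% (0.049), 28.9% to 29.4% (0.050).

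**The case against.** The strongest defence is that nothing is inflated. A Bonferroni split between two looks is valid and needs no information fraction. That suits a design in which interim OS is triggered by PFS events and final OS by follow-up time, with no planned interim death count. This stands. A reader might infer from the re-test that the 0.05 is not protected; step 1 and the table show the reverse.

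Second, the plan can be read as letting an interim win stand. Protocol 4.4.2 and 12.1 say that OS meeting its allocated level can make the study formally positive, interim OS has its own allocated level, and no text lets a later look revoke it. SAP section 11 also leaves monitoring guidelines to a DSMB charter that is not among the documents. This is a fair reading, but it leaves the re-test levels in Figure 1 without a purpose, and an inference is weaker than a stated rule for the key secondary endpoint.

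Third, the contradiction is rare. That also stands. The 10% is conditional on a win that itself occurs in under 3% of trials, and it belongs to a branch that needs ORR positive and a failed PFS test.

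A reader might also conclude that alpha released by an interim OS win ought to go to PFS. At 0.050 rather than 0.040, 3rd line+ PFS power would be 91.6% rather than 90.0%, but only after an interim win with ORR positive. It would also make the co-primary level, and its fixed 96% interval, depend on OS. That is a design preference, and the documents do not show its absence to be an error.

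**Conclusion.** The point holds as a correction to a rule. Figure 1 re-tests an already rejected OS null at 0.009, 0.010, 0.049 or 0.050 and has no rule for a failed re-test. The negative-interim levels of 0.008 and 0.048 leave about 0.0005 to 0.0019 of OS alpha unspent.

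The consequences are small. Type I error is controlled, conservatively; the contradiction has a probability of about 0.3% or less at hazard ratio 0.828 and the derived fraction; and the OS power forgone is about 0.3 to 1 point. The documents do not support reading this as a threat to the trial's error control or as a likely reversal of the OS result.

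The sizes rest on the SAP's OS medians, exponential survival, eta = 2 accrual, no dropout, and a derived interim count of about 160 deaths. The structural fault depends on none of these. Protocol Figures 2 and 3 are not shown and could not be compared. Priority: low.

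**What to change.** 1. Delete the final-test levels from all positive-interim cells of Figure 1. State in SAP 8.2 and 8.3 that rejection of the OS null at the interim is final, and that the later OS analysis is then reported as an estimate with a 95% confidence interval and no further test.
2. After a negative interim, keep the interim level at 0.001 or 0.002. Obtain the final level from the bivariate normal distribution with correlation √(observed interim deaths / observed final deaths), so that total OS alpha equals 0.009, 0.010, 0.049 or 0.050. At a fraction of 0.71 the levels are about 0.0087, 0.0093, 0.0490 and 0.0499. State the OS total in each branch in place of the 0.008 to 0.05 range.
3. Make matching changes in protocol 12.3.7.2 and 12.3.7.3 and the synopsis. Check Figures 2 and 3: the Overall Population plan quotes the same 0.008 to 0.05 range, and 0.040 + 0.002 + 0.008 = 0.050 suggests the same return of interim alpha to OS.

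Passing released OS alpha to PFS is optional and not part of this fix.

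Cost: a redrawn figure, a few sentences, and a protocol amendment, since protocol 12.1 requires one when methods for key secondary hypotheses change. No extra patients, looks or data are needed, and family-wise error stays at or below 0.05. The change should be made before any OS data are compared by arm.
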